## CLINICAL TRIAL SUMMARY

COMPOUND: Sarilumab	STUDY No.: SARILL08755 STUDY NAME: SariPRO
TITLE	Effect of sarilumab on patient-reported outcomes in patients with moderately to severely active rheumatoid arthritis and with inadequate response or intolerance to current conventional synthetic DMARDs or TNF inhibitors
INVESTIGATOR/TRIAL LOCATION	Mainland France
PHASE OF DEVELOPMENT	Phase IV
	STUDY OBJECTIVES
STUDY DESIGN	
SariPRO is a national, multicenter, open-label, single-arm phase IV study.
 
Four study periods are defined for this study period:
 
 
• Screening period: within 28 days prior to study treatment start (Baseline visit, Day 1), patient eligibility is determined at the Screening visit. At Baseline visit, patient's inclusion in the study is established.
 
• 6-month core period: patients who fulfil the enrollment criteria received a SC injection of sarilumab 200 mg every 2 weeks as monotherapy and/or in combination with methotrexate (MTX) or csDMARD(s) (at investigator's discretion) for 24 weeks. Patient visits are scheduled at W4, W12, and W24.
 
• LTE period: all the patients who will complete the 6-month-core-period are allowed to continue the treatment with sarilumab, every 2 weeks for a maximum of another 24 weeks or until the commercial availability of sarilumab in France, depending whichever comes first. Patient visits are scheduled every 12 weeks over the LTE period (at W36 and W48).
 
• Post-treatment follow-up: each patient will have one follow-up visit, between 2 and 4 weeks after his/her last administration of sarilumab.
 

STUDY POPULATION Main selection criteria (6-month core period)	
Inclusion criteria:
 
 
• Adult patients (≥18 years) with moderately to severely active RA according to the American College of Rheumatology (ACR)/European League against Rheumatism (EULAR) 2010 Rheumatoid Arthritis Classification Criteria
 
• Patients with moderate to severe disease activity of
 

	
RA defined as a DAS28-ESR >3.2 at Screening
 

• Patients with inadequate response within at least the last 3 months or intolerance to current csDMARD or to at least one anti-TNF therapy (as defined by the investigator)

• Oral corticosteroids (<math>\leq 15</math> mg/day prednisone or equivalent) and NSAIDs or COX-2 (up to the maximum recommended dose) are allowed if at a stable dose for at least 4 weeks prior to Baseline

• Permitted csDMARDs are allowed if at a stable dose for at least 4 weeks prior to Baseline

• Females of childbearing potential can participate in this study only if using a reliable means of contraception during the study and for at least 3 months following the last dose of sarilumab

• Female of childbearing potential must have a negative pregnancy test at the Screening and Baseline visits

• Patients must have signed a written informed consent prior to perform any study-related procedures.

 
Exclusion criteria:
 

• Rheumatic autoimmune disease other than RA or prior history or current inflammatory joint disease other than RA

• Treatment with any investigational agent within 4 weeks of Screening

• Last RA treatment prior to inclusion with any antiJAK or biologic DMARD other than anti-TNF

• Patients treated with anti-TNF (e.i. adalimumab, infliximab, certolizumab, golimumab, etanercept) before the screening period, which are maintained within the 4 weeks before the inclusion (i.e.the first injection of sarilumab)

• Intra-articular or parenteral corticosteroids within 4 weeks prior to Baseline

• History of severe allergic or anaphylactic reactions to human, humanized, or murine monoclonal antibodies (or to any of the excipients associated to sarilumab)

• Stage III or IV cardiac failure according to the New York Heart Association classification

• Evidence of active malignant disease, malignancies diagnosed within the previous 10 years (except basal and squamous cell carcinoma of the skin or carcinoma in situ of the cervix uteri previously excised and cured)

• Patient who is institutionalized due to regulatory or legal order or patient who is mentally disabled or educationally disadvantaged

• History of previous gastrointestinal perforation or diverticulitis

• Known active current/ recurrent infections (including

--	---

	
B and C hepatitis)
 
NOTE: in case of latent TB infection the patient may be included if a subsequent appropriate anti TB treatment is initiated since at least 3 weeks
 
 
• Active tuberculosis or history of incompletely treated tuberculosis
 
• Evidence of serious uncontrolled concomitant disease, including severe uncontrolled hypercholesterolemia or hypertriglyceridemia at Screening
 
• Hemoglobin <8.5 g/dL at Screening
 
• Creatinine clearance <30 mL/min at Screening
 
• White blood cells <3000/mm^3 at Screening
 
• Absolute neutrophil count <2000/mm^3 at Screening
 
• Absolute lymphocyte count <500/mm^3 at Screening
 
• Platelet count <150 000 cells/mm^3 at Screening
 
• AST or ALT >1.5 x ULN at Screening
 
• Total bilirubin >ULN at Screening, unless Gilbert's disease has been determined by genetic testing and has been documented
 
• Total fasting cholesterol >3.50 g/L [9.1 mmol/L] or triglycerides >5.00 g/L [5.6 mmol/L] at Screening.
 

Total expected number of patients	140 patients enrolled in 35 university hospitals and general hospitals centers are expected throughout mainland France.
STUDY TREATMENT(s)	
Investigational medicinal product(s)	Sarilumab, anti-IL6R mAb (anti-interleukin 6 receptor monoclonal antibody)
Formulation:	Single-use prefilled glass syringes of sarilumab 200 mg (and 150 mg in case of laboratory abnormalities)
Route(s) of administration:	Subcutaneous (SC) route, in abdomen, thigh, or upper arm
Dose regimen:	Sarilumab 200 mg is to be administered every 2 weeks (q2w) over the both treatment periods (as monotherapy or in combination with a csDMARD according to the investigator decision).
Non-investigational medicinal product(s)	NA
Formulation:	
Route(s) of administration:	
Dose regimen:	
Post-trial access to study medication	NA


ENDPOINTS
	
Primary endpoint (6-month core period):
 
Change in the total RAID score from baseline to Week24
 
Secondary efficacy endpoints (6-month core period):
 
 
• Values at each assessment visit and changes from baseline for the total RAID score, HADS, MATHys, FACIT-Fatigue, HAQ-DI, morning stiffness, International Physical Activity Questionnaire, and patient global assessment of disease activity
 
• Values at each assessment visit and changes from baseline for ESR, DAS28-ESR, CDAI, and joint counts (TJC, SJC)
 
• DAS28-ESR Low Disease Activity (LDA) and remission, CDAI LDA and remission, at W12 and W24
 
 
Safety endpoints (6-month core and long-term extension periods):
 
 
• Incidence and severity of adverse events (AEs), serious and non-serious AEs, AESIs, AEs leading to dose modification or treatment withdrawal, AEs leading to death
 
• Physical examination, vital signs, and clinically significant laboratory abnormalities over time.
 


ASSESSMENT SCHEDULE
	
The study will consist of the following visits:
 
 
• Visit 1 (D-28-D-1): screening
 
• Visits of the 6-month core period:             
 
• Visit 2 (D1): baseline, first sarilumab administration
 
• Visit 3 to 5 at W4, W12, and W24, respectively: on treatment
 
 
 
• Visits of the LTE period (if applicable)             
 
• Visits LTE 1 and LTE 2 at W36 and W48, respectively: on treatment
 
 
 
• Visit PT: post treatment.
 
 
At screening and at baseline visits, a physical examination to assess disease activity and general health will be performed. Patients will be assessed for active or latent tuberculosis (TB) at baseline and during the study. For an overview of the local laboratory tests, see the study flowchart below, which include hematology, chemistry, and lipids. A serum pregnancy test for women of childbearing potential will be obtained at Screening as well.
 
PROs (RAID, HADS, MATHyS, FACIT-Fatigue, HAQ-DI, duration of morning stiffness, IPAQ, and patient global assessment of disease activity) will be assessed (completed by patients before all other assessments performed during the 6-month core study visits) at Baseline, Week 4, Week 12, and Week 24, as well as efficacy assessments (ESR, DAS28-ESR, CDAI, and joint counts (TJC, SJC, on 28 joints for both counts).

[figure not shown]

	
Safety assessments are performed at each assessment visit during the 6-month core period (and over the LTE period if applicable) and at the post-treatment visit. They include Adverse Events, Serious Adverse Events, and Adverse Events of Special Interest including symptomatic overdose and pregnancy.
 
Patients and Investigators must respect the visit schedule per study flowchart. If a visit date is changed, the next visit should take place according to the original schedule.


STATISTICAL CONSIDERATIONS
	
Sample size determination:
 
According to the literature and previous studies having assessed sarilumab, the standard deviation (SD) of the RAID score could be estimated at 2.5 points. On this basis, a sample size of 140 included patients in order to have at least 112 evaluable patients (assuming almost 20% of non-evaluable patients), produces a precision, two-sided 95% confidence interval (CI), with a distance from the mean to the limits that will be less than 0.5 (considering 20% non-evaluable patients) when the estimated SD is 2.5, assuming that the change from baseline will be from 30% to 50% of baseline score.
 
Analysis populations:
 
 
• Intent-to-treat (ITT) population: all patients who met the eligibility criteria and who are actually treated.
 
• Safety population: all patients who have signed the Informed Consent Form (ICF) and have been exposed to at least one dose or part of a dose of IMP.
 
• Per-protocol population: patients of ITT population without major protocol deviations.
 
 
Primary analysis:
 
The primary study objective is to assess the change in RAID score from baseline to W24.
 
The number of available data, mean, standard deviation, median and range (minimum, maximum) will be provided with the 95% confidence interval of the mean change from baseline to W24. Main analysis will be performed on ITT population. Sensitivity analysis will be conducted in reproducing the same analysis using the per-protocol population.
 
In addition, multivariate analyses such as ANCOVA, Logistic Regressions and Multiple Correspondences analysis can be performed from baseline in order to exploratory explain patient profiles.
 
Analysis of secondary endpoints:
 
All secondary parameters will be described; 95% CI will be provided.

DURATION OF STUDY PERIOD (per patient)	The total duration of the core study period per patient is expected to be approximately 32 weeks: 

• Up to 4-week screening

• 24 weeks treatment

• 2-4 week post-treatment observations.

 For patients who will enter in the LTE period, a maximum of another 24 weeks is planned.
---	--

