### 5.2 SECONDARY (6-MONTH CORE PERIOD)

- To assess the change of the RAID score from baseline (to W4, W12, and W24) in patients with moderately to severely active RA and inadequate response or intolerance to current csDMARD or TNF inhibitors, treated with sarilumab in combination with csDMARD and/or monotherapy.
- To assess the effect of sarilumab in combination with csDMARD and/or monotherapy on other patient-reported outcomes (global assessment of disease activity, disability, morning stiffness, fatigue, anxiety/ depression, mood disorders, and physical activities), in patients with moderately to severely active RA and inadequate response or intolerance to current csDMARD or TNF inhibitors.
- To assess the efficacy of sarilumab in combination with csDMARD and/or monotherapy using DAS28-ESR and CDAI in patients with moderately to severely active RA and inadequate response or intolerance to current csDMARD or TNF inhibitors.
- To assess the safety of sarilumab in combination with csDMARD and/or monotherapy in patients with moderately to severely active RA and inadequate response or intolerance to current csDMARD or TNF inhibitors.

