#### **9.2.1.2 Values at each assessment visit and changes from baseline for ESR, DAS28-ESR, CDAI, and joint counts (TJC, SJC)**

At each visit, all the efficacy parameters will be assessed.

The **erythrocyte sedimentation rate (ESR)** is measured in mm/hr. This laboratory test will be performed in a local medical laboratory.

The DAS28 is a combined index for measuring disease activity in RA. The index includes the assessment of 28 joints for swelling and tenderness, acute phase response (ESR or CRP), and general health status. For this study, ESR will be used to calculate the DAS28 score. The index is calculated using the following formula:

$$\mathbf{DAS28-ESR} = 0.56 \times \sqrt{(TJC28)} + 0.28 \times \sqrt{(SJC28)} + 0.70 \times \ln(ESR) + 0.014 \times PtGA$$

where **TJC28** is the tender joint count on 28 joints, **SJC28** is the swollen joint count on 28 joints,  $\ln$  is the natural log, ESR is the erythrocyte sedimentation rate (mm/hour), i.e., patient's global assessment of disease activity (PtGA using a 100 mm VAS). The 28 joints to be assessed are detailed in Appendix B.

The DAS28 scale ranges from 0 to 10, where higher scores represent higher disease activity.

The **CDAI** is a combined index for measuring disease activity in RA that does not include a laboratory test. It is calculated as follows:

$$\text{CDAI} = \text{TJC28} + \text{SJC28} + \text{PtGA (in cm)} + \text{PhGA (in cm)}$$

where TJC28 is the tender joint count on 28 joints, SJC28 is the swollen joint count on 28 joints, PtGA is patient's global assessment of disease activity (100mm VAS), and PhGA is the physician's global assessment of disease activity (100mm VAS). The 28 joints to be assessed are detailed in Appendix B.

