### **9.2.1.3 DAS28-ESR Low Disease Activity (LDA) and remission, CDAI LDA and remission, at W12 and W24**

A DAS28-ESR score of <2.6 represents clinical remission and a score of  $\leq 3.2$  represents low disease activity.

A CDAI score of  $\leq 2.8$  represents clinical remission and a score of  $\leq 10.0$  represents low disease activity.

For both indexes, clinical remission is included in low disease activity.

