### Infections

Biologics including sarilumab have been associated with an increased risk of infections. Physicians should then exercise caution when considering the use of sarilumab in patients with a history of recurring infections or with underlying conditions (e.g., diabetes mellitus) which may predispose patients to infections. Sarilumab should not be administered in patients with active infection. Therefore patients with active current infection or a history of recurring infection (including but not limited to active TB or history of incompletely treated TB and atypical mycobacterial disease, hepatitis B and C, and herpes zoster) will be excluded from the study.

The effects of sarilumab on acute reactants, neutrophils, and the signs and symptoms of infection should be considered when evaluating a patient for a potential infection. Any infection should be reported by the Investigator as an adverse event and a corresponding eCRF form should be filled in (type of infection, treatment with antibiotics if any with route of administration).

As all biologics, sarilumab may induce immunosuppression, increasing the risk of reactivation of latent TB. As a precautionary measure, patients with active TB will be excluded from the study. For inclusion, patient with a past history of TB could be included only if there is a documented confirmation medically validated by the Investigator that the patient was adequately treated and does not meet any of the TB-related exclusion criteria, notably based on physical examination, negative chest X-ray and TB test over the Screening period.

**NOTE:** in case of latent TB infection the patient may be included if a subsequent appropriate anti TB treatment is initiated since at least 3 weeks

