APPENDIX A: DERIVED DATA

The derived data are variables which are calculated from the raw data in the CRF/eCRF and not included in the database (e.g.: AUC, total score, duration, summary value from repeated observations, study exposure, study drug exposure, study drug cumulative dose, etc.).

The formula used for derived data should be provided and examples may be necessary to clarify the calculation. The strategy for missing data must be specified in the calculation of derived data (e.g.: the minimum number of observations required to calculate an average score, handling incomplete dates).

All references used to calculate the derived data should be mentioned below.

The following derived data will be calculated and included in the listings:

(1) SUBGROUPS DECISION

Treatment started before screening visit and ongoing at screening visit	Prescribed treatment at baseline
csDMARDs	Sarilumab + csDMARDs
Biological therapy	Sarilumab + csDMARDs
csDMARDs or biological therapy	Sarilumab in monotherapy

(2) DAS28-ESR

$DAS28-ESR = 0.56 \times \sqrt{TJC28} + 0.28 \times \sqrt{SJC28} + \ln(ESR) + 0.014 \times PtGA$ (in mm)

Where:

- ln is the natural logarithm
- SJC is the swollen joints
- TJC is the tender joints
- PtGA is the patient's global assessment of disease activity (using a 100 mm VAS)
- ESR is the erythrocyte sedimentation rate (mm/h)

(3) CDAI

$CDAI = TJC28 + SJC28 + PtGA(\text{in cm}) + PhGA(\text{in cm})$

Where:

- SJC is the swollen joints
- TJC is the tender joints
- PhGA is the physician's global assessment of disease activity (using a 100 mm VAS)
- PtGA is the patient's global assessment of disease activity (using a 100 mm VAS)

(4) BMI

BMI (kg/m²) will be derived as $\text{Weight (kg)} / [\text{Height (cm)} / 100]^2$ and rounded to the nearest decimal.

(5) Time between baseline and initial diagnosis (years)

Time between baseline and initial diagnosis in years will be calculated as $(\text{initial diagnosis date} - \text{baseline visit date} + 1) / 365.25$.

(6) Changes from baseline (V2)

Absolute variation (points) from baseline will be calculated as a difference from baseline (e.g. assessment at the visit – assessment at baseline).

Relative variation (%) from baseline will be calculated as: $((\text{assessment at the visit} - \text{assessment at baseline}) / \text{assessment at baseline}) * 100$.

If necessary, evolution will be presented according to decision tables from Appendix B.

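### DAS28-ESR and CDAI response rates are unranked, although DAS28-ESR contains ESR and the protocol acknowledges that sarilumab affects acute-phase reactants

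*Protocol*

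**What the plan says.** The secondary objective in Protocol 5.2 is "To assess the efficacy of sarilumab in combination with csDMARD and/or monotherapy using DAS28-ESR and CDAI", and SAP 1.2.2 repeats it. The endpoint list in the Clinical Trial Summary gives "DAS28-ESR Low Disease Activity (LDA) and remission, CDAI LDA and remission, at W12 and W24". SAP 5.1.3 lists LDA and remission under each index, and SAP 5.3.2.3 presents the secondary endpoints with 95% CIs. None of these places ranks the two indices or says how to read them if they disagree.

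Protocol 9.2.1.2 states "For this study, ESR will be used to calculate the DAS28 score" and ends the formula with "0.70 \times \ln(ESR) + 0.014 \times PtGA". The same section classes ESR as an acute-phase measure and says of CDAI that it "is a combined index for measuring disease activity in RA that does not include a laboratory test". SAP Appendix A, item (2), ends its DAS28-ESR formula with "\ln(ESR) + 0.014 \times PtGA"; no coefficient stands before the logarithm.

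Protocol 9.2.1.3 sets the cut-offs: "A DAS28-ESR score of <2.6 represents clinical remission", with LDA at 3.2 or below. For CDAI, remission is 2.8 or below and LDA is 10.0 or below.

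Protocol 10.6, under Infections, gives this caution for suspected infection only: "The effects of sarilumab on acute reactants, neutrophils, and the signs and symptoms of infection should be considered when evaluating a patient". No efficacy or analysis section carries that caution over to DAS28-ESR.

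**The concern.** A drug that blocks IL-6 signalling may lower an acute-phase marker by more than the patient's joints and symptoms improve. Any such excess enters DAS28-ESR through ln(ESR) and cannot enter CDAI. If the indices then disagree, the plan does not say which one governs, and the report could lead with the higher rate.

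Separate summaries of ESR, joint counts and each index show that a divergence exists. They do not show which patients met the DAS28-ESR cut-off without meeting the CDAI one. At stake is the trial's statement on disease activity, which is a named secondary objective.

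**Working it through.** The plan states no figure to reproduce here, so the check uses its own formulas and cut-offs.

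**Inputs.** Protocol 9.2.1.2: DAS28-ESR = 0.56 x sqrt(TJC28) + 0.28 x sqrt(SJC28) + 0.70 x ln(ESR) + 0.014 x PtGA (mm), and CDAI = TJC28 + SJC28 + PtGA (cm) + PhGA (cm). Protocol 9.2.1.3: the cut-offs above. Protocol 7.1: entry requires DAS28-ESR above 3.2. The ESR values are assumptions, shown as a range, because the documents give none.

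**Step 1: ESR alone.** With everything else fixed, the fall in DAS28-ESR is 0.70 x ln(ESR before / ESR after), and the change in CDAI is 0.
- ESR 20 to 5: 0.70 x ln(4) = 0.97
- ESR 40 to 5: 0.70 x ln(8) = 1.46
- ESR 40 to 2: 0.70 x ln(20) = 2.10

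**Step 2: fold-fall in ESR needed to cross a cut-off.** This is exp[(start - cut-off) / 0.70].
- From 3.2 to the remission boundary at 2.6: exp(0.6/0.70) = 2.36-fold
- From 3.5: 1.54-fold for LDA, 3.62-fold for remission
- From 4.0: 3.14-fold and 7.39-fold
- From 5.1: about 15-fold and 36-fold

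ESR alone can therefore matter for patients not far above the entry threshold, and is unlikely to suffice in high disease activity. The term is additive, however, so it also adds to any real clinical improvement.

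**Step 3: one patient.** TJC 3, SJC 3, PtGA 40 mm and PhGA 40 mm, all unchanged. CDAI = 3 + 3 + 4 + 4 = 14 throughout, which is not LDA. The part of DAS28-ESR without ESR is 0.970 + 0.485 + 0.560 = 2.015.

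| ESR (mm/h) | DAS28-ESR, protocol formula | DAS28-ESR, SAP formula |
|---|---|---|
| 40 | 4.60 | 5.70 |
| 10 | 3.63 | 4.32 |
| 5 | 3.14 (LDA) | 3.62 |
| 2 | 2.50 (remission) | 2.71 (LDA) |

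Under the protocol formula this patient reaches LDA only when ESR is at or below exp[(3.2 - 2.015)/0.70] = 5.4, a fall of about 86%. A 75% fall, to 10, is not enough.

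**Step 4: the SAP formula.** Without the 0.70, an ESR-driven change is 1/0.70 = 1.43 times as large (ESR 40 to 5: 2.08 instead of 1.46). The score itself is also higher by 0.30 x ln(ESR) at any ESR above 1, so LDA and remission become harder to reach. The omission thus enlarges the ESR part of mean change while lowering response rates. At maximal joint counts and PtGA, the part without ESR is 2.963 + 1.482 + 1.400 = 5.845. The SAP version then passes the 0 to 10 range stated in Protocol 9.2.1.2 once ESR exceeds exp(10 - 5.845), about 64. The protocol version does so only at about 378.

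**The case against.** The best defence is that the plan already contains the remedy. CDAI LDA and remission are patient-level rates without ESR at the same visits, and ESR, joint counts and patient global assessment are each described. All analyses are descriptive without tests (Protocol 11.4.2.3), no secondary endpoint has priority over another, and RAID contains no ESR. Most of this stands and limits the weight of the point. It does not supply a rule for disagreement between the indices, or a patient-level view of it.

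The size is also unknown. Protocol 10.6 speaks of acute reactants; it does not name ESR, give a direction or magnitude, or say that the effect is independent of clinical response. Some of any ESR fall will be genuine improvement. This stands too.

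Three stronger readings are tempting, and the documents do not support them.
- A reader might infer from the MONARCH table in Protocol 4.1.2 that inflation is already demonstrated, since the sarilumab/adalimumab ratio is 26.6/7.0 = 3.8 for DAS28-ESR remission but only 71.7/58.4 = 1.2 for ACR20. The same table gives 3.28/2.20 = 1.49 for DAS28-ESR mean change, close to 0.61/0.43 = 1.42 for HAQ and 45.7/29.7 = 1.54 for ACR50. Ratios also rise with the stringency of the criterion (ACR70: 23.4/11.9 = 2.0). In MOBILITY, which used DAS28-CRP, remission (34.1/10.1 = 3.4) matches ACR70 (24.8/7.3 = 3.4). TARGET, also DAS28-CRP, does show a gap (28.8/7.2 = 4.0 against 16.3/7.2 = 2.3). The picture is mixed.
- A reader might blame the single-arm design. A control arm on a drug that does not block IL-6 would not remove an ESR effect specific to sarilumab.
- A reader might ask for LDA and remission recomputed with ESR frozen at baseline. That applies the 3.2 and 2.6 cut-offs to an index for which the protocol does not define them, and discards ESR change that reflects real response.

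**Conclusion.** The point holds as one of interpretation and reporting. Two indices carry the disease-activity objective unranked. One contains a marker of the class that the protocol says the drug affects, and the other contains no laboratory test. DAS28-ESR LDA and remission could overstate clinical benefit; the documents do not show that they will.

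The formula fixes the mechanism (1.46 points for ESR 40 to 5, with CDAI unchanged), but the effect on the trial's rates cannot be computed without an ESR distribution. The reading assumes that sarilumab's acknowledged effect on acute reactants includes ESR and is not wholly explained by clinical improvement.

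The change is worth making but does not threaten the trial: the affected endpoints are secondary and descriptive, CDAI is already derived, and RAID is unaffected. The differing DAS28-ESR formulas are a definite discrepancy whatever one thinks of the rest. They also bear on the exploratory models in SAP 5.3.2.5, which use DAS28-ESR as a covariate.

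**What to change.** First, reconcile the DAS28-ESR formula in SAP Appendix A, item (2), with Protocol 9.2.1.2.

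Then, in Protocol 9.2.1.3 and SAP 5.1.3 and 5.3.2.3:

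1. State that the disease-activity conclusion rests on CDAI LDA and remission, with DAS28-ESR LDA and remission supportive because of the acute-phase effect.
2. Add a table at W12 and W24 cross-classifying patients by DAS28-ESR and CDAI status, for LDA and for remission, showing those who respond on DAS28-ESR only. These patients should not be labelled false responders, since the indices differ in more than ESR.
3. Report the ESR contribution to mean DAS28-ESR change, 0.70 x [ln(ESR at visit) - ln(ESR at baseline)], beside the total change.

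All of this uses data already collected and leaves visits and sample size alone. The cost is some SAP wording, one extra table and one derived quantity. The headline disease-activity rate may look less favourable.
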